4.6.2. Secondary efficacy endpoints

The following secondary efficacy endpoints will be studied.

- 1) Responder rate at 12 weeks
Responder rate at 12 weeks will be presented in the same way as for the primary endpoint with exception of the sensitivity analysis using the PPS. Missing assessments at 12 weeks will be imputed using the LOCF approach.
- 2) Time to first response
Time to first response will be analyzed using a Kaplan-Meier (KM) method ([Kaplan 1958](#)). Patients without response will be considered censored at their last assessment of the (adjusted) INCAT disability score. Patients with a non-allowed treatment intake before a first response will be considered censored at the date of the first intake of a forbidden treatment. KM estimates of the mean, median as well as the first and third quartile will be provided together with their associated 95% confidence interval. Reason for censoring will be also indicated. A KM-plot will be provided showing the incidence of a first response over time. Time of censoring will be displayed in the graph. A table will be included below the graph showing the number of patients "at risk" (i.e. without a first response), the number of patients with a first response and the number of censored patients at the time points 0, 6, 12, 18 and 24 weeks. Descriptive statistics will be provided for the time to first response on the subset of patients with response until EOS.
- 3) Percentage of patients at 12 weeks and EOS visit with no change in CIDP treatment
The number and % of patients without change in CIDP treatment will be presented at 12 weeks and at the EOS visit. The associated exact 95% Clopper-Pearson CI will be calculated. A change in CIDP treatment is defined as at least one of the following conditions:

Average dose (g/kg) (see section [5.7.3](#)) of the course is not within 5% of the theoretical study treatment dose (g/kg)

- Theoretical dose is 2 g/kg at the first course and 1 g/kg at subsequent courses for patients with a BMI <30 kg/m²
- Theoretical dose is 1.6 g/kg at the first course and 0.8 g/kg at subsequent courses for patients with a BMI ≥30 kg/m²
- Decrease of the time between courses
 - Time between day 1 of a course and day 1 of the following course is less than 14 days
- Addition of corticosteroids (equivalent of more than 10 mg/day of prednisone for more than 10 days) or immunosuppressive drugs. As this condition is not possible to derive by programming, the study physician will review all treatments with corticosteroids and immunosuppressive drugs prior to database lock and flag those who fulfil the condition.
- Premature discontinuation of study drug due to insufficient response to IMP and start of another CIDP treatment, corticosteroids, immunosuppressive drugs or plasma exchange

A listing will provide details about the nature of the CIDP treatment changes.

4) Adjusted INCAT disability score

The adjusted INCAT disability score will be presented with descriptive statistics at each visit. The change from baseline in the adjusted INCAT disability score will be analyzed at 12 weeks and EOS visit.

Several graphics will be produced:

- Boxplots over time of a) the at-visit values and b) change from baseline
- Waterfall plots faceted by visit of a) the at-visit values and b) change from baseline

5) Grip strength (kPa) with the Martin vigorimeter in both hands

Actual and normalized (according to the healthy population [Merkies 2000](#)) grip strength will be presented with descriptive statistics at baseline, week 12 and EOS for the dominant hand and the non-dominant hand side by side. The change from baseline in grip strength for the dominant hand and the non-dominant hand will be analyzed at 12 weeks and at the EOS visit. The assessment at screening will be used for the determination of the dominant hand. Normalization according to a healthy population is calculated using the formula (see Section [5.7.5](#)).

6) Rasch-built Overall Disability Scale (R-ODS)

R-ODS will be presented with descriptive statistics at baseline, week 12 and EOS visit. The change from baseline in R-ODS will be analyzed at 12 weeks and at the EOS visit.

7) Medical Research Council (MRC) 12 muscles sum score (0 to 5)

The MRC sum score will be presented with descriptive statistics at baseline, week 12 and EOS visit. The change from baseline in MRC score will be analyzed at 12 weeks and at the EOS visit.

8) Rasch-modified MRC (0 to 3)

The Rasch-modified MRC sum score will be presented with descriptive statistics at baseline, week 12 and EOS visit. The change from baseline in Rasch-modified MRC score will be analyzed at 12 weeks and at the EOS visit.

9) Patient and Investigator Clinical Global Impression (CGI)

The CGI-S (*Severity of illness*) assessment by patients and investigators will be presented side by side with descriptive statistics at the visits baseline, week 12 and EOS for the categories *Normal*,

not at all ill / Borderline ill / Mildly ill / Moderately ill / Markedly ill / Severely ill / Among the most extremely ill patients (only for the investigator judgment). A shift table will be provided for the change from baseline at week 12 and EOS.

The CGI-I (*Improvement*) assessment by patients and investigators will be presented side by side with descriptive statistics at the visits week 12 and EOS for the categories *Very much improved / Much improved / Minimally improved / No change / Minimally worse / Much worse / Very much worse*.

The CGI-E (*Efficacy index*) assessment by patients and investigators will be presented with descriptive statistics at the visits week 12 and EOS in a 4×4 cross-table crossing Therapeutic effect categories (*Marked / Moderate / Minimal / Unchanged or Worse*) with Side effect categories (*None / Do not significantly interfere with patient's functioning / Significantly interferes with patient's functioning / Outweighs therapeutic effect*). The sum over the number and % of patients shown the 4×4 cross-table (16 cells) will correspond to the number of patients with valid assessments and 100% respectively. The cross-table will also show a row and column with the Total for each dimension corresponding to the separate description of the Therapeutic effect and the Side effects.

For the endpoints 4) to 8) the one sample Hodges-Lehmann estimator ([Hodges 1963](#) and [Han 2008](#)) and the associated 95% confidence interval will be calculated for all at-visit values, as well as for the change from baseline to 12 weeks and EOS visit for both the overall and patient subgroups. The change from baseline for the endpoints 4) to 8) will be tested using a one sample Wilcoxon signed-rank test, for the overall set of patient only. All statistical tests will be descriptive and will use a two-sided significance level of $\alpha=5\%$.

Statistical tests will not be performed by subgroup.

For all secondary efficacy endpoints, assessments performed after the use of a non-allowed treatment will be censored (not used in the statistical summaries).

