12.9.1. Primary Efficacy Variable(s)

12.9.1. 1. Description of the primary efficacy variable(s)

The primary efficacy endpoint will be the responder rate at EOS visit.

Responder patients are defined as patients with a decrease of at least 1 point in the adjusted INCAT disability score between baseline and the EOS visit.

If a patient is treated with a not-allowed treatment during the study period, then all efficacy variables measured after the intake of these not-allowed treatments will be censored for the efficacy analyses.

12.9.1. 2. Hypothesis Test and Primary Analysis Model

The responder rate will be tested against the historical responder rate of 33.3% with a one-sided Clopper-Pearson test (exact binomial test) at the nominal level of significance of 2.5%.

The null and alternative hypotheses are as follows:

$$H_0: \pi_{(110E)} \leq 33.3\%$$

$$H_a: \pi_{(110E)} > 33.3\%$$

The proportion of responders and the associated 95% confidence interval will be estimated using a Clopper-Pearson method. The primary analysis will be performed on the FAS.

12.9.1. 3. Handling of Missing Data

The primary analysis of the primary criterion will be done using the baseline and last available assessment of the adjusted INCAT disability score after the first study drug administration. If the score at EOS visit is missing, then the Last Observation Carried Forward (LOCF) approach will be applied and the last available adjusted INCAT disability score will replace the missing value at EOS visit. Other imputation methods might be defined in the SAP for the purpose of sensitivity analyses.

12.9.1. 4. Prognostic factors and covariates

No prognostic factors will be used in the statistical model.

12.9.1. 5. Other analyses for the primary variable

The analysis of the primary criterion will be repeated on the PPS as sensitivity analyse.

Other sensitivity analyses might be defined in the SAP.

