2.3. Sample Size

The study is designed to demonstrate superiority of I10E to an historical control in terms of responder rate. The historical responder rate with placebo is estimated from the ICE study ([Hughes RA 2008](#)). As a conservative estimate the upper boundary of the 95% confidence interval (CI) of the observed rate is used (observed rate $12/58 = 20.7\%$, 95% CI [11.2%, 33.3%]). Based on this historical placebo responder rate of 33.3% and a 60% responder rate with I10E, 38 evaluable patients are needed in order to obtain 90% power using an exact binomial test with a one-sided nominal level of significance $\alpha=2.5\%$. Presuming 10% non-evaluable patients, 42 patients will be included in the study (around one third of all patients will be either Immunoglobulin [Ig]-naïve or relapsing Ig-pre-treated).

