3.2. Handling of Missing Data and Outliers

Regarding the primary criterion, a patient will be also considered as a non-responder if the patient is withdrawn due to lack of efficacy of the treatment (insufficient response to the investigational medicinal product [IMP]). In all other cases, if the INCAT score at EOS visit is missing, then the Last Observation Carried Forward (LOCF) approach will be applied and the last available adjusted INCAT disability score will replace the missing value at EOS visit.

The LOCF approach will also be used to handle the missing data of the secondary endpoint for adjusted INCAT and response at week 12 only.

When AEs are documented in the diary, dates of AE onset may be missing and as a result, TAAE cannot be defined. For AEs with a missing or incomplete start date, the response to the question “Did the AE start within 72 hours of an infusion” will be used for determining if the AE is temporally related to the infusion.

Partial dates of first symptoms and partial dates of diagnosis will be imputed by 15 if only the day is unknown and by 1st July if day and month are unknown. No imputation will be done if the year is unknown.

For the calculation of duration of AEs, partial start and end dates will be imputed with the first and last possible date within the period defined by the partial date, respectively. In general, no

calculation of duration will be made if either the start date or stop date is missing, i.e., cannot be imputed using pre-determined rules. No other general rules for the replacement of missing data are planned.

Data listings will always show the original CRF reported values and not the imputed values.

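### Time to first response: censoring patients who leave for insufficient response, or who start forbidden treatment because CIDP worsens, biases the Kaplan-Meier incidence of response upward

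*SAP*

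**What the plan says.** SAP 4.6.2 item 2 analyses time to first response by Kaplan-Meier, with two censoring rules. The general rule is "Patients without response will be considered censored at their last assessment of the (adjusted) INCAT disability score". The rule for rescue is "Patients with a non-allowed treatment intake before a first response will be considered censored at the date of the first intake of a forbidden treatment". Withdrawal for insufficient response is not excepted from the general rule, and no competing-event or sensitivity analysis is planned. Reasons for censoring are to be reported, censoring times shown on the plot, and numbers at risk, responded and censored tabulated at 0, 6, 12, 18 and 24 weeks. Protocol 12.9.2.2 asks only for a Kaplan-Meier method, and for INCAT scores after a forbidden treatment to be left out.

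The primary endpoint treats the same patients differently. Under SAP 3.2, "a patient will be also considered as a non-responder if the patient is withdrawn due to lack of efficacy of the treatment". Under SAP 4.6.1, after a forbidden treatment the last score before intake stands in for the EOS score. A patient who had not yet responded at intake is therefore a non-responder in the primary as well.

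Protocol 5.4 lets the investigator stop study drug when the adjusted INCAT score rises 1 point above baseline and a change of treatment is judged mandatory, or when it rises by at least 2 points. Its examples of a changed treatment (another IVIg, corticosteroids, immunosuppressants, plasma exchange) largely coincide with the forbidden treatments listed in SAP 4.6. Protocol 3.1.5 puts the EOS visit within 7 days of discontinuation, so such a patient's last INCAT assessment falls early, not at week 24.

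**The concern.** Kaplan-Meier estimates the incidence of response correctly only if a patient censored at a given time has the same later chance of responding as those still at risk. A patient who leaves because of worsening, or is rescued for it, is a poor match for that assumption. Removing such patients from the risk set passes their weight to the patients who stay, and the curve rises at every later response.

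What is at stake is the reported curve, median and quartiles. The error runs in one direction, in favour of I10E. In a single-arm, open-label trial there is no control curve carrying the same error against which to judge it.

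**Working it through.** **The plan's own figure.** The documents give no planning figure for time to response. The only related one is the sample size in SAP 2.3: "38 evaluable patients are needed in order to obtain 90% power", for a true rate of 60% tested against 33.3%. With n = 38 the exact test rejects at 19 or more responders: P(X ≥ 19 | 0.333) = 0.0244 and P(X ≥ 19 | 0.60) = 0.9216. At n = 37 the power is 0.892, and no n from 34 to 37 reaches 90%. The figure reproduces, and nothing below touches it.

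**Inputs to the illustration.**
- INCAT visits every 3 weeks from week 3 to week 21, then EOS at week 24 (Protocol 10.1.1 and the study plan).
- 42 patients, the planned number included (SAP 2.3).
- Assumed: first responses of 4, 6, 5, 4, 2, 1, 1 at weeks 3, 6, 9, 12, 15, 18, 21, so 23 responders and 19 patients who never respond.
- Assumed: m of those 19 exit early, split equally between two times. SAP 4.1 plans to count withdrawals for insufficient response, but no expected number is given.

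**Formula.** S(t) = product over response times of (1 − d/n), where d is the number of first responses and n the number at risk; the reported incidence is 1 − S(24).

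**Exits held as non-responders to week 24.** Whatever m is, S(24) = 19/42 and the incidence is 23/42 = 54.8%.

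**SAP rule, 4 exits at weeks 4 and 7.** The numbers at risk become 42, 36, 28, 23, 19, 17, 16:

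S(24) = (38/42)(30/36)(23/28)(19/23)(17/19)(16/17)(15/16) = 0.404, incidence 59.6%.

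**SAP rule, 4 exits at weeks 13 and 16.** S(12) = 23/42; then 21, 17 and 16 are at risk at weeks 15, 18 and 21:

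S(24) = (23/42)(19/21)(16/17)(15/16) = 0.437, incidence 56.3%.

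The same product for other counts gives the week-24 incidence in %:

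| Exits | weeks 4/7 | weeks 10/13 | weeks 13/16 | held to week 24 |
|---|---|---|---|---|
| 0 | 54.8 | 54.8 | 54.8 | 54.8 |
| 2 | 57.0 | 56.0 | 55.5 | 54.8 |
| 4 | 59.6 | 57.4 | 56.3 | 54.8 |
| 6 | 62.5 | 59.0 | 57.3 | 54.8 |
| 8 | 65.8 | 61.1 | 58.5 | 54.8 |

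**Median** (first visit with S ≤ 0.5). It is week 15 with no exits. It moves to week 12 only with 6 or 8 exits at weeks 4/7, and stays at week 15 in every other cell.

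**Sensitivity to the assumed pattern.** With 38 patients and 23 responders (60.5%), using a front-loaded and an even spread of responses and exits between about weeks 3.5 and 15.5, 4 exits give 63.0-67.1% and 8 exits 67.3-75.7%. In the even pattern, 4 exits can move the median from week 21 to week 18; in the front-loaded pattern, 4 exits leave it at week 12. The direction is stable; the size is not.

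**The case against.** The best defence is that this is a recognised choice, openly reported. Estimating response as if no rescue had been given is a legitimate aim, Protocol 12.9.2.2 names Kaplan-Meier, and the SAP shows reasons, times and numbers of censoring. SAP 4.1 tabulates withdrawals for insufficient response, and treatment change is an endpoint of its own. SAP 3.4 calls secondary analyses purely descriptive. In the illustration the shift is small beside the sampling error: the exact 95% interval for 23/42 is 38.7% to 70.2%.

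Much of this stands and limits the point's weight. It does not remove the point. Even when the aim is response without rescue, Kaplan-Meier needs censored patients to resemble those remaining, and Protocol 5.4 suggests that they do not. Disclosure lets a reader suspect the problem but leaves the printed curve and quartiles as they are.

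A reader might infer four stronger things that the documents do not support:
- *That the SAP contradicts itself.* The non-responder rule in SAP 3.2 is confined to the primary criterion. This is inconsistent handling across two endpoints.
- *That the curve should equal the primary responder rate.* First response at any visit and response at EOS differ by definition. A patient who responds and later loses the response is an event in one and a non-responder in the other, and cumulative incidence would not remove that gap.
- *That every forbidden treatment is a failure.* The list includes blood products and systemic corticosteroids, which may be given for reasons other than CIDP.
- *That the week-12 responder rate is also wrong.* Item 1 does say "Missing assessments at 12 weeks will be imputed using the LOCF approach", but also that the rate is presented as for the primary, which can be read as importing the non-responder rule. At most that is ambiguous. A patient withdrawn for INCAT worsening is a non-responder under LOCF anyway.

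**Conclusion.** The point holds, as an upward bias in one descriptive secondary analysis that depends on such exits occurring. Arithmetically, each early exit by a non-responder raises 1 − S if anyone responds afterwards. Calling the excess a bias rests on failing patients having a lower later chance of response than those who stay, which Protocol 5.4 makes plausible.

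In the 42-patient pattern the excess over 54.8% runs from 0.7 points (2 exits at weeks 13/16: 55.5 − 54.8) to 11.0 points (8 exits at weeks 4/7: 65.8 − 54.8). Exit counts, exit times and response pattern are all assumed, because the documents give none of them. With no such exits the bias is zero. The median is less sensitive and in this pattern needs 6 or more very early exits to move. The primary test, its alpha and the sample size are unaffected.

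**What to change.** In SAP 4.6.2 item 2, make the main display the cumulative incidence of first response, with the median and quartiles read from that curve. Treat two events before a first response as competing: withdrawal for insufficient response, and forbidden treatment started because of CIDP. Holding these patients at risk as non-responders to week 24 gives the same point estimate when there is no other early censoring.

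Item 3 already has the study physician review corticosteroid and immunosuppressant use before database lock. Extend that review to every forbidden treatment taken before a first response, and record whether it was given for CIDP. Keep censoring where it was given for another reason. Keep the planned Kaplan-Meier analysis, labelled supportive, and declare the change in SAP 4.10.

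The cost is small: another estimator on data already collected, plus a modest extension of a planned review. The drawbacks are a slightly less favourable curve if such exits occur, and a declared departure from Protocol 12.9.2.2.

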8.2.7. Visit 11: Week 24 (+/- 7 days) - End of study visit

At the end of the 24-week treatment and follow-up period, patients undergo an end of study visit evaluation. This visit occurs 3 weeks after the 7th course of study drug at a dose of 1 g/kg.

In the event of premature discontinuation from the study drug or patient withdrawal from the study, an end of study visit is performed within 7 days.

The end of study assessment should be performed before any other treatment including Igs is administered.

The reason for premature study drug discontinuation / study withdrawal should be accurately assessed and entered into the eCRF.

The following study procedures will be carried out:

- Complete physical examination.
- Biometric information: weight.
- Vital signs: temperature, heart rate, systolic and diastolic blood pressure.
- Neurological status assessment:
 - INCAT disability score (adjusted INCAT disability score will be deduced from reported values).
 - Patient and Investigator CGI-S, CGI-E and CGI-I.
 - MRC sum score.
 - Rasch-modified MRC sum score.
 - R-ODS.
 - Grip strength with Martin vigorimeter in both hands.
- Biological tests in local laboratory:
 - Haematology:

- Complete blood count + differentials, Hb, MCV, platelets count.
- Haptoglobin.
- Reticulocytes, direct Coombs test
- Biochemistry:
 - Creatininemia, glomerular filtration rate according to MDRD.
 - LDH.
 - Total and free bilirubin (total bilirubin in all patients; if total bilirubin > ULN, free bilirubin will be assessed from the same blood sample, as total bilirubin).
 - AST, ALT, ALP, γ GT.
 - Total serum protein level.
 - C3 and C4 antigens.
 - Serum total IgG trough levels.
- HBs Ag, anti HBs & anti HBc Ab, HIV, HCV tests.
- Serum reference sample for long term storage.
- Urine protein reagent strip test [to be performed before study drug administration in patients who at screening tested for urine protein reagent strip result "1 cross 1 (+) and/or had GFR in the range of 60-80 mL/min/1.73m²]:

If urine protein reagent strip test result = Negative or Trace	Action: No further urine test required
If urine protein reagent strip test result = 1 cross (1 +) or more	Action: Assess either AER or PER from a 24h-urine collection sampled at least 7 days after the end of the previous study drug course or assess ACR or PCR from a spot urine sample immediately following the urine protein reagent strip test (i.e. urine obtained before study drug administration).

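### SAP 4.6.2 plans a Kaplan-Meier mean time to first response with no stated time horizon, so if the curve stays above zero the printed mean is an area cut at an unspecified point

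*SAP*

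**What the plan says.** SAP 4.6.2 item 2 analyses time to first response by Kaplan-Meier. On the summary statistics it states: "KM estimates of the mean, median as well as the first and third quartile will be provided", each with a 95% confidence interval.

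On censoring it states: "Patients without response will be considered censored at their last assessment of the (adjusted) INCAT disability score". Patients who take a non-allowed treatment before responding "will be considered censored at the date of the first intake of a forbidden treatment". For a completer the last assessment is the end-of-study (EOS) visit, which Protocol 8.2.7 places at week 24, plus or minus 7 days.

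Item 2 also plans a Kaplan-Meier plot with censoring times marked, the reasons for censoring, and a table under the plot that includes "the number of censored patients at the time points 0, 6, 12, 18 and 24 weeks". A responder-only summary is planned as well: "Descriptive statistics will be provided for the time to first response on the subset of patients with response until EOS".

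Protocol 12.9.2.2 asks for a Kaplan-Meier method and does not mention a mean, so the mean is an addition made in the SAP. SAP 5.2 names SAS 9.4. Neither document gives a restriction time, a truncation rule for the mean, or a restricted-mean label.

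**The concern.** A Kaplan-Meier mean is the area under the curve of patients still without a response. It estimates the mean time to response only if the curve reaches zero. If patients without a response are censored at about week 24, the curve normally ends above zero. The area then has to be cut somewhere, and the part beyond the cut is left out.

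The SAP does not say where the cut falls. The printed mean and its interval therefore refer to a horizon that the reader is not told. Someone who takes the figure as the average time to respond will read it as shorter than the unrestricted mean. If the cut is the last observed response, two datasets with similar early response can also be summarised over different lengths of follow-up. Nothing confirmatory is at stake, but a mean with an interval is the kind of figure that gets quoted on its own.

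**Working it through.** **Inputs from the documents.** Non-responders are censored at the last INCAT assessment (SAP 4.6.2). INCAT is assessed at weeks 3, 6, 9, 12, 15, 18, 21 and 24 after the first course (SAP 2.6; Protocol 8.2.4 to 8.2.7). The design assumption in SAP 2.3 is: "Based on this historical placebo responder rate of 33.3% and a 60% responder rate with I10E, 38 evaluable patients are needed". The documents give no figure for the mean time to response and no distribution of response times, so the timing below is assumed.

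**The plan's own figure.** With 38 patients, the exact test against 33.3% succeeds at 19 or more responders, with one-sided level 0.0244 and power 0.922 at 60%. No smaller number reaches 90% power, so 38 is reproduced. It is used here only as the source of the 60%.

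**Formula.** Mean to time t = sum over intervals up to t of (length of interval) × S, where S is the proportion without a first response.

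**Example A (assumed).** There are 42 patients. First responses occur at weeks 3 (10 patients), 6 (6), 9 (4), 12 (3) and 15 (2), and 17 patients are censored at week 24.

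- Patients without a response during the five successive 3-week intervals to week 15: 42, 32, 26, 22, 19. From week 15 on: 17.
- Cut at the last response (week 15): 3 × (42 + 32 + 26 + 22 + 19)/42 = 423/42 = 10.07 weeks.
- Extended to week 24: 10.07 + 9 × 17/42 = 10.07 + 3.64 = 13.71 weeks.
- If one of the 17 first responds at week 24, the last-response figure becomes 13.71 weeks. The last-observation figure is 13.71 weeks in both cases.

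**Example B (assumed).** 60% respond, spread evenly over the visits to week 12, and the rest are censored at week 24.

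- Cut at the last response: 3 × (1 + 0.85 + 0.70 + 0.55) = 9.3 weeks.
- Cut at 24 weeks: 9.3 + 12 × 0.40 = 14.1 weeks.
- If the remaining 40% responded at week 36, the full mean would be 14.1 + 12 × 0.40 = 18.9 weeks. If at week 48, it would be 14.1 + 24 × 0.40 = 23.7 weeks. The data to week 24 cannot tell these apart.

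**Simulation, constant response rate (assumed), 38 patients, p responding by week 24.** The unrestricted mean is −24/ln(1 − p).

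| p | Unrestricted mean (weeks) | Average KM mean, cut at last response | Average KM mean, cut at last observation | Shortfall |
|---|---|---|---|---|
| 60% | 26.2 | 16.4 | 16.6 | 37% |
| 70% | 19.9 | 14.9 | 15.1 | 24–25% |
| 80% | 14.9 | 13.0 | 13.1 | 12–13% |

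Both cuts fall short, and here they differ by only 0.1 to 0.2 weeks.

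**How much the last-response cut moves.** This depends on the late tail.

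- 60% responding, mostly early with a thin late tail: the last response falls at week 12 in 10% of simulated trials, week 15 in 21%, week 18 in 31%, week 21 in 17% and week 24 in 20%. The last-response mean averages 11.5 weeks, with a central 95% range of 7.9 to 15.8 that includes ordinary sampling variation. The 24-week mean averages 13.8 weeks.
- 60% responding, all by week 12: the cut is at week 12 in 99% of trials, and the range is 7.7 to 10.0 weeks.

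**Visit window.** With EOS visits spread over plus or minus 7 days, the latest observation can itself be a response. The curve then drops to zero and no cut is made. This occurred in about 8% of simulated trials at 60% responding and 17% at 80%, purely because of visit dates.

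**Third quartile.** With 60% responding by a common week-24 visit, it is reached in about 3% of simulated trials.

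**The case against.** Several counter-arguments have force.

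- **The 60% belongs to another endpoint.** It is the assumed rate of response at EOS. Item 2 counts a first response at any visit, so a patient who responds at week 6 and has lost the response by EOS is an event here. The share never responding may be well under 40%, and the gap narrows accordingly (14.9 against about 13.0 weeks at 80%). This stands. The curve need only stay above zero for the mean to lose its meaning, and it normally does at 80% too.
- **The cut rule is not in the documents.** A reader might infer from Example A that one late responder will move the reported mean by weeks. The documents do not support that as a general consequence. It requires a last-response cut, which the SAP does not state, and responses that stop well before week 24.
- **The mean may exist.** A reader might infer that no true mean exists, or that the interval covers nothing at all. Neither follows. Non-response at week 24 leaves the mean unidentified from these data, not absent, and the interval does have a target, the area to the cut, which the SAP fails to name.
- **Too short compared with what?** In Example A the average among the 25 responders is (10×3 + 6×6 + 4×9 + 3×12 + 2×15)/25 = 168/25 = 6.7 weeks, less than the 10.1 printed. The shortfall is relative to the unrestricted mean only, and the responder-only figure is planned separately.
- **Other displays protect the reader.** The median, quartiles, plot, risk table and reasons for censoring would show a plateau. SAP 3.4 calls secondary analyses purely descriptive. This stands, and it keeps the point minor.

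**Conclusion.** The point holds as a minor defect in one descriptive statistic. Unless nearly everyone responds, or the latest observation happens to be a response, the planned mean is an area with an unstated end point. It falls below the unrestricted mean under either cut, by 37% at 60% responding and 12–13% at 80% if the response rate is constant. Dependence on the date of the last response is a further problem only under a last-response cut, and its size then varies with the late tail. All these sizes rest on assumed response timing. A mean to a prespecified, labelled horizon would be a valid summary, but the SAP does not define one. The primary test, the sample size and the analysis sets are unaffected.

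**What to change.** In SAP 4.6.2 item 2, replace the Kaplan-Meier mean with the restricted mean time to first response up to a fixed 24 weeks, labelled as such, with its 95% confidence interval. Alternatively, delete the mean. Keep the median and quartiles, and print 'not reached' where the curve does not get there. If the restricted mean is kept, state whether times are nominal visit weeks or actual dates, because an EOS visit can fall up to a week after week 24.

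For orientation, if responses are spread evenly over visits to week 9, 12, 18 or 24, the 24-week restricted mean would be 13.2, 14.1, 15.9 or 17.7 weeks at 60% responding, and 9.6, 10.8, 13.2 or 15.6 weeks at 80%.

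The cost is about one sentence in the SAP and a small programming change. No new data are needed, and the protocol need not change because it does not ask for a mean.
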